Description of Study Agent/Procedure	Treatments include silver diamine fluoride (SDF), fluoride varnish (FV), and resin-modified glass ionomer cement (GIC) sealants to prevent caries. SDF is also provided to arrest caries. GIC can also be used to arrest caries, and when used for this purpose, is called atraumatic restoration, or ART. SDF and ART can also be provided in combination, which is referred to as silver modified atraumatic restorative technique (SMART). We will also provide participants with an electronic toothbrush. For interventions using SDF, one drop (0.05 ml) of SDF solution at 38% concentration (2.24 F-ion mg/dose) will be dispensed per child. Posterior tooth surfaces to be treated will be dried, and the SDF will be applied with a microbrush to all asymptomatic cavitated lesions and to all pits/fissures on bicuspid and molar teeth for 30 s. For interventions using sealants and/or ART, glass ionomer sealants will be applied to all pits and fissures of bicuspid and molars, and placement of ART on all frank asymptomatic cavitated lesions. For Silver Modified Atraumatic Restorative Technique, SDF will be applied as described above on any carious tissue, followed by glass ionomer cement for restoration. Auto-cure GIC will be used to reduce SDF/sealant stain. For FV, a 5% NaF solution will be applied to all teeth after application of SDF or ART.
Reference Therapy	As a sequential, multiple-assignment, randomized trial, there is no reference therapy beyond standard of care (dental sealants), as described above.
Key Procedures	Full-mouth visual-tactile oral examination, SDF application, FV application, dental sealant application.
Statistical Analysis	For objective 1, we will use generalized linear mixed models followed by marginal causal excursion effect estimation. For objective 2, we will use augmented inverse probability weighting (AIPW) with marginal structural models (MSM) and Q-learning. For objective 3, we will use microcosting in tandem with time studies.

Schematic of Study Design

Observation and Treatment Schedule

Observation	Procedures	Estimated Time
0-months (Time 1)	Initial treatment, SDF or sealant	Fall 2026
6-months (Time 2)	Tailoring observation, second line treatment	Spring 2027
12-months (Time 3)	Tailoring observation, second line treatment	Fall 2027
18-months (Time 4)	Outcome Observation	Spring 2028
24-months (Time 5)	Outcome Observation	Fall 2028
30-months (Time 6)	Outcome Observation	Spring 2029

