Subgroup Size and Interventions

Subgroup A	N = 420	Silver diamine fluoride (single application)
Subgroup B	N = 90	Silver diamine fluoride (initial treatment) followed by SDF reapplication plus FV plus electronic toothbrushing
Subgroup C	N = 90	Silver diamine fluoride (initial treatment) followed by GIC sealant application and silver modified atraumatic restorations
Subgroup D	N = 420	GIC sealants (single application)
Subgroup E	N = 90	GIC sealants (reapplication, as ART) followed by FV plus electronic toothbrushing
Subgroup F	N = 90	Add SDF as silver modified atraumatic restorative treatment

1 Key Roles

Principal Investigator

[name] [name], MPH; Associate Professor
New York University
[name]
[name]
[contact]
[contact]

Clinical Director (Sub-Investigator)

[name] [name], MPH; Research Scientist
New York University
[name]
[name]
[contact]
[contact]

Research Scientist (Sub-Investigator)

[name]; Assistant Professor
New York University
[name]
[name]
[contact]
[contact]

Site PI

To Be Determined

NIH Program Director

[name]
Supervisory Team Lead, Integrative Biological and Environmental Sciences
National Institute on Minority Health and Health Disparities
[name]
[contact]
[contact]

2 Introduction, Background Information and Scientific Rationale

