- ii. Soft Tissue Irritation: Accidental application to gingival or mucosal tissues may result in temporary irritation, typically resolving within 3-7 days.
- iii. Staining of Carious Lesions: SDF permanently stains carious lesions dark brown or black, which may have cosmetic implications. However, this staining indicates that the lesion has been arrested.
- iv. Temporary Skin Staining: If spilled on the skin, SDF can cause a temporary brown discoloration, lasting up to two weeks. Immediate washing with soap and water reduces the staining.

b. Long-Range Risks:

- i. Cosmetic Impact of Staining: The permanent dark staining of arrested carious lesions may have psychosocial effects in participants who are concerned about aesthetics.
 1. Mitigation: The application of silver diamine fluoride is limited to carious lesions on the back teeth, in keeping with previous study findings that indicate staining on posterior teeth is more acceptable than staining on anterior teeth, and oral-health related quality of life in children receiving silver diamine fluoride is non-inferior to those receiving sealants and ART at least 6 months post-treatment.

c. Rationale for the Necessity of Exposing Participants to These Risks:

- i. The study aims to provide non-invasive, cost-effective, and Medicaid-reimbursable dental care for underserved populations. The benefits of preventing and arresting tooth decay outweigh the minimal risks involved.

d. Why the Value of the Information Gained Outweighs the Risks:

- i. The study will generate real-world evidence on the effectiveness of SDF in school-based settings, which is critical for improving oral health programs, especially for underserved populations.

e. Alternative Procedures Considered:

- i. Traditional restorative, surgical dental treatment (e.g., fillings, crowns) was not selected due to its invasiveness, high cost, risk of pain, infection, and need for anesthesia.

2. Fluoride Varnish (PreviDent and FluoroDose)

a. Immediate Risks:

- i. Nut Allergy Consideration: Some fluoride varnish formulations contain pine nut derivatives.
 - 1. Mitigation: FluoroDose (nut-free formulation) will be used for individuals with nut allergies, and PreviDent will be used for individuals without nut allergies.
 - ii. Mild Irritation: In rare cases, fluoride varnish may cause transient gum or mucosal irritation, which typically resolves within 24 hours.
- b. Long-Range Risks: n/a

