6.1.5 Dosing and Administration

Doses are not weight-based. All products are administered by licensed dental professionals or trained study staff under clinical supervision during the clinical visit which takes place during traditional school hours. There are no self-administered components.

1. Advantage Arrest: 1-2 drops are dispensed to a dappen dish or mixing well and applied per site with a microbrush, once per lesion or sound tooth. Application time: ~30 seconds scrubbing with a minimum 1-minute drying time.
2. Fluoride Varnish: Applied to all tooth surfaces post-cleaning. 0.3-.4mL per child. Applied with brush, allowed to set with saliva.
3. GC Fuji IX: Mixed and placed into cavities using appropriate applicators and finger-sweep technique. Sets chemically in under 6 minutes.

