6.3.1 Administration of Procedural Intervention

All interventions will be administered by licensed dentists or dental hygienists. Any individuals administering the intervention (those individuals providing care as part of the SCHOOL-BASED DENTAL PROGRAM) will be first added to the study and approved as investigators prior to their involvement.

Each visit will last approximately 7-12 minutes, on average. Fluoride varnish may be reapplied at 6-month intervals. Silver diamine fluoride and sealants or ART with Fuji IX will be placed during the initial and subsequent 6-month intervals, with bi-annual evaluation for retention and replacement as needed, in line with protocol. At least 5 visits are proposed for participants in this study.

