7.1 Study Procedures/Evaluations

All treatments listed in the schematic for the BASICS experimental study are already provided by participation in the school-based caries prevention program. Thus, procedures described in section 7.1.1 are already established

in the program. In this proposed study, we will be changing the order of treatments based on the longitudinal oral health needs of participants. Thus, the research component of this study is to explore the impact of the variation in treatment scheduling and sequence on oral health.

All of the included procedures can be expected to be provided outside of the study, but the study specific procedures will modify the order of the procedures that are provided.

7.1.1

Study Specific Procedures

While the following procedure are provided as part of the operations of the SBCP, they are included as study-specific as well as these are the accepted procedures for the treatments selected for the study.

At each study visit, a clinician will perform full-mouth visual-tactile oral examinations using a disposable mirror, disposable explorer, and head lamp with participants laying in a portable dental chair. Teeth will be assessed as being present or missing intraorally. Individual tooth surfaces will be assessed as being intact/sound, sealed, restored, decayed, or arrested. Caries diagnosis will use the International Caries Detection and Assessment System (ICDAS) scoring criteria for 5 (distinct cavity with visible dentine) or 6 (extensive distinct cavity with visible dentine) [27, 28].

At the baseline observation, the enrolled population will be randomized to receive a first-stage treatment of either silver diamine fluoride (Trajectory 1) or dental sealants with atraumatic restorations, where indicated (Trajectory 2). Children in the initial SDF group will receive the treatment on sound posterior dentition and any posterior teeth with untreated decay. Children in the sealant and ART group will receive either treatment on posterior dentition based on the presence of untreated caries. In both groups, treatment will be applied in the absence of pain, abscess, or infection

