Nonresponse will be determined at the second and third post-baseline observational periods by the diagnosis of any dental caries on posterior dentition, including any new caries on previously sound dentition (primary prevention failure) or any teeth diagnosed at baseline with caries that failed to demonstrate arrest (secondary prevention failure). The total number of caries will also be recorded. Responders to either first stage treatment will continue to receive biannual screenings for retention and responsiveness. Non-responders will subsequently proceed to second-stage randomization.

Nonresponders in Trajectory 1 will receive a second-stage randomization to either SDF reapplication plus fluoride varnish receipt of an electronic toothbrush, or an SDF reapplication plus dental sealants. As nonresponse is determined by the diagnosis of new caries, this latter pathway will take the form of delayed silver-modified atraumatic restorative treatment (delayed SMART) [22, 23] on any affected teeth and application of sealants to any remaining sound dentition. Similarly, nonresponders in Trajectory 2 will be randomized to either an augmented treatment of sealant reapplication (including atraumatic restorations) plus fluoride varnish and receipt of an electronic toothbrush or an intensified protocol of SMART on affected dentition. Caries incidence will continue to be evaluated at each remaining planned observation.

Additional design procedures include (1) any patients with sealants that are not retained but no decay is indicated will be considered responsive and the sealant will be reapplied; (2) any patients with atraumatic restorations that are not retained will be considered non-responsive, as it cannot be robustly determined if there is no new decay; (3) any responding participant who transitions to nonresponse after the predetermined nonresponse periods will continue to receive their original first-stage intervention and the total days that elapsed before nonresponse was observed will be recorded; (4) any nonresponding patient who continues to fail to respond will receive reapplication/reinforcement of their second-stage intervention; (5) any new dentition that erupts in either Phase 1 or Phase 2 will receive the corresponding treatment for that phase (e.g., first-stage or second-stage randomized treatment).

7.1.2

Standard of Care Study Procedures

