7.8 Rescue Medications, Treatments, and Procedures

Should children experience caries are treatment with SDF or dental sealants, we will provide SDF (for caries management), atraumatic restorations, or silver modified atraumatic restorative treatment.

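### The first-stage regimens are not uniquely defined: the protocol contradicts itself on how often SDF and sealants are applied, how much SDF is dispensed and which teeth receive it

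*Protocol*

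**What the plan says.** **Frequency.** The table of subgroup sizes and interventions gives A as "Silver diamine fluoride (single application" and describes D, the sealant responders, in the same way. Section 7.1.1 has responders return twice a year for checks. It adds retreatment only in set cases: a lost sealant is replaced, newly erupted teeth are treated, and a child who first fails after the nonresponse window "will continue to receive their original first-stage intervention". Section 6.3.1 says "Silver diamine fluoride and sealants or ART with Fuji IX will be placed during the initial and subsequent 6-month intervals", without separating arms or responders from nonresponders. Section 2.4.2 says, under both SDF and glass ionomer, that all participants receive prevention twice yearly. Section 6.1.9 allows single or twice-yearly application and refers back to the protocol. The Schedule of Events marks dispensation at Visits 1 to 6.

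**Amount.** The Protocol Summary says "one drop (0.05 ml) of SDF solution at 38% concentration (2.24 F-ion mg/dose) will be dispensed per child". Section 6.1.5 says "1-2 drops are dispensed to a dappen dish or mixing well and applied per site with a microbrush".

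**Target teeth.** Section 2.4.1, as mitigation for staining, says "The application of silver diamine fluoride is limited to carious lesions on the back teeth". Section 7.1.1 says "Children in the initial SDF group will receive the treatment on sound posterior dentition and any posterior teeth with untreated decay". The Protocol Summary and section 6.1.5 also include sound teeth.

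**Caries after treatment.** Section 7.8 says "we will provide SDF (for caries management), atraumatic restorations, or silver modified atraumatic restorative treatment". It names no arm, visit or randomization. Section 7.1.1 re-randomizes nonresponders found at Visits 2 and 3, keeps late nonresponders on first-stage treatment, and repeats the second-stage treatment in those who go on failing.

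**The concern.** The trial's stated research question is the effect of treatment schedule and sequence, so the schedule is the intervention. If clinicians at about 12 schools can take different schedules from the same protocol, what is delivered may vary by school or provider, and the randomized contrast no longer refers to one pair of treatments.

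The analysis plan cannot repair this afterwards, because it does not govern what is done at the chair. Intention-to-treat keeps the arms comparable as randomized, but it does not say which treatment policy the estimate describes.

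The conflicts over amount and target teeth matter less for the contrast. They do mean that the risk text and the treatment text describe SDF exposure differently, and parents may be relying on wording drawn from either.

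**Working it through.** **1. How many children the frequency conflict touches.** Inputs: 1200 children split equally between first-stage arms (600 each, the sum of each trajectory in the subgroup table) and 30% average nonresponse (section 10.5).
- Nonresponders per arm: 600 × 0.30 = 180, or 90 in each of B, C, E and F.
- Responders per arm: 600 × 0.70 = 420, in A and in D.
- These reproduce the table exactly. A + D = 840, and 840 / 1200 = 70%.

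**2. What the readings imply.** The visits fall at 0, 6, 12, 18, 24 and 30 months.
- Under the subgroup table, a responder has one placement, apart from the exceptions in section 7.1.1.
- Under section 6.3.1 read literally, placement could occur at up to six visits. Care at Visit 6 is listed after that visit's examination, so at most five placements could affect a recorded outcome.
- Nonresponse is also judged at Visit 3. A child who responds at Visit 2 has been retreated before that judgement under one reading and not under the other. The reading could therefore affect who reaches second-stage randomization.

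**3. Which analyses depend on it.**
- The first-stage contrast in section 10.5 is A+B+C against D+E+F. Of the 600 children on each side, 420 are in A or D.
- Section 4.1 embeds four regimes, each a pair of pathways: A with B, A with C, D with E, D with F. Each contains A or D.
- Section 10.4.3 values resources as unit cost times quantity used per patient, so material cost moves directly with the number of placements.
- Section 6.3.3 checks clinicians by comparing records with the pathway in the research design. That check needs one written pathway.

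**4. Amount of SDF.** The fluoride table in section 2.2 gives 0.05 ml per drop and 44.8 mg fluoride per ml.
- One drop: 0.05 × 44.8 = 2.24 mg, matching the Protocol Summary.
- Two drops: 0.10 × 44.8 = 4.48 mg, twice the stated per-child figure. This takes 1-2 drops as the amount dispensed per child at a visit, which section 6.1.5 does not say outright.

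**5. Target teeth.** For a caries-free child in the SDF arm, section 2.4.1 as worded describes no SDF exposure. Section 7.1.1, section 6.1.5 and the Protocol Summary describe exposure on sound posterior teeth. The passages cannot all be accurate for that child.

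**6. Section 7.8 against section 7.1.1.** Read literally, section 7.8 permits SMART, which distinguishes C and F, for a child in B or E. It also permits ART or SMART for a late nonresponder in the SDF arm, whom section 7.1.1 keeps on SDF. Section 7.8 does not say that assignment takes precedence.

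**The case against.** The strongest reply is that section 7.1.1 already sets out a working algorithm: two first-stage options, four second-stage options and five numbered rules for special cases. That stands. A reader might infer that the regimens are not defined at all, but the text does not support this. They are defined in one place and contradicted in others.

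On frequency, the sentence in section 6.3.1 goes on to mention evaluation and replacement as needed, in line with protocol, and section 6.1.9 has similar wording. Both sections cover all subgroups, and nonresponders do receive later placements. Twice-yearly checks without retreatment fit a single application, and dispensation at every visit could reflect replacements and second-stage care. The Observation and Treatment Schedule labels the 18- to 30-month visits as outcome observations, so six placements is the extreme reading. All this softens the conflict without resolving it. The qualifier points back to a document that says both things, and section 2.4.2 promises twice-yearly prevention to everyone. The design figure is not shown in the text reviewed and may favour one reading, but the written passages would still disagree.

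On target teeth, the sentence in section 2.4.1 addresses staining and mainly argues posterior against anterior teeth, while the treatment passages agree with one another. It would go too far to infer that caries-free children in the SDF arm might go untreated, since the same section says no child will. What stands is that the risk wording does not match the treatment wording.

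On section 7.8, its list matches the caries treatments used across the assigned pathways, so it may be a loose summary, and the late- and persistent-nonresponse rules in section 7.1.1 are explicit. A reader might infer that it erases the B+E against C+F contrast. The documents support only that it could dilute that contrast if taken literally.

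On drops, both passages give an amount dispensed, so 4.48 mg is not a stated dose received. Section 2.4.1 gives no SDF amount, so this mismatch does not make the risk section wrong.

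**Conclusion.** The point holds in this form: the first-stage regimens are not uniquely defined, because sections that instruct clinicians contradict one another. Frequency is the substantive conflict. It covers 840 of 1200 planned children, the first-stage contrast, the responder branch of all four embedded regimes, the costing and the fidelity check. The count of 840 rests on the protocol's 30% nonresponse assumption and would move with the actual rate.

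The amount of SDF dispensed (up to two-fold) and the target teeth are real contradictions with less effect on the comparison. Section 7.8 is an ambiguity.

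No sample-size or power figure depends on these conflicts, and none should be reopened because of them. The review takes no position on which schedule, amount or target is correct.

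**What to change.** Reconcile the Protocol Summary, the subgroup table, sections 2.4.1, 2.4.2, 6.1.5, 6.1.9, 6.3.1, 7.1.1 and 7.8, and the Schedule of Events to one regimen per subgroup, stated identically in each. For every subgroup, say at which visits each product is placed, on which teeth and in what amount, and which retreatments belong to the regimen. State how section 7.8 relates to second-stage randomization and to the late- and persistent-nonresponse rules in section 7.1.1. Then check the consent text against the result. The clinical team decides the content.

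No new deviation or analysis rule is needed: sections 6.3.3 and 14.3 already cover mismatches and deviations, and sections 10.3 and 10.4.2 already specify intention-to-treat.

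The cost is protocol wording, and consent wording if the risk or exposure description changes, with the IRB review that any amendment needs. Do this before the first treatments, estimated for Fall 2026, because divergent delivery cannot be corrected later.

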2.1 Background Information and Relevant Literature

As the world's most prominent noncommunicable disease [1], dental caries experience affects over 70% of children in the United States [2, 3]. A known determinant of caries is a lack of access to preventive and therapeutic care [4], resulting in disproportionate burdens of disease in low-income and minority children [2, 3]. Persistent untreated dental caries in children can lead to pulpal involvement, dental abscess, oral pain, and systemic infection [5, 6], and the effects of dental caries are not limited to dental and craniofacial health. Prior evidence shows that poor oral health is negatively associated with school attendance and academic achievement [7], with some estimates attributing up to thirty million hours of lost seat time per year due to dental issues [8], and those with untreated disease face negative impacts on oral health-related quality of life and psychosocial functioning.

School-based approaches for caries prevention, such as school sealant programs, are clinically and cost-effective interventions [9] and the Association of State and Territorial Dental Directors (ASTDD) reports that over 65% of states in the US have active school sealant programs [10]. Similarly, school fluoride initiatives can prevent caries

in permanent teeth [11] and are particularly effective in areas without community water fluoridation [12], and more comprehensive programs providing sealants, fluoride varnish, and atraumatic restorations can control existing caries and reduce their further incidence [13]. Silver diamine fluoride has also emerged as a promising addition to the school dental program portfolio, controlling existing caries and preventing new decay when applied along with fluoride varnish [14].

Despite this overall effectiveness, it is consistently observed that approximately 1 in 4 children participating in school caries prevention fails to respond to care, subsequently presenting with recurrence or first incidence of caries. For example, an open prospective cohort of children receiving comprehensive prevention showed that 20% of children consistently developed caries regardless of whether they were disease free or not at baseline [13], while data from school-based pragmatic trials observed that 24% to 36% of children receiving silver diamine fluoride (SDF) or glass ionomer sealants developed new caries sometime after receiving care [15, 16]. Prior etiologic studies of this treatment nonresponse to select preventive interventions demonstrated that there are innate microbial and environmental factors that may be related to the responsiveness to school-based care. In children receiving SDF, the salivary microbiome showed that separate clusters of bacterial species were enriched or depleted in responders compared to nonresponders [17], and machine learning models suggest that *Prevotella pallens* and *Veillonella dentocariosa*, as well as diet and hygiene behavior, may be useful in predicting nonresponse [18].

Chairside solutions are needed as an interventional strategy to mitigate treatment nonresponse in school-based caries prevention. The Building Adaptive School-based Interventions for Caries Study (BASICS) will develop and test dynamic treatment regimes (DTR) for patient nonresponse [19], incorporating elements of precision medicine into school caries prevention [20]. As a pragmatic trial, BASICS will be implemented in collaboration with an existing school-based caries prevention program (SBCP), known as SCHOOLYARD SMILES (SYS). SYS already provides the listed interventions to be studied in BASICS, but the order of receipt will change according to the experimental design. Following completion of the study, de-identified data from SBCP/BASICS participants will be provided to investigators for analysis.

In this protocol, the SBCP and SYS will be referred to interchangeably.

